2 STUDY OBJECTIVES

2.1 Primary Objective

The **primary objective** is to examine the effects of saxagliptin on myocardial and hepatic fat content in patients with impaired glucose tolerance (IGT).

2.2 Secondary Objectives

The secondary objective is to examine the effect of saxagliptin on left ventricular systolic and diastolic function and monocyte inflammation in patients with IGT

3 ETHICAL CONSIDERATIONS

3.1 Good Clinical Practice

This study will be conducted in accordance with Good Clinical Practice (GCP), as defined by the International Conference on Harmonisation (ICH) and in accordance with the ethical principles underlying European Union Directive 2001/20/EC and the United States Code of Federal Regulations, Title 21, Part 50 (21CFR50).

The study will be conducted in compliance with the protocol. The protocol, any amendments, and the subject informed consent will receive Institutional Review Board/Independent Ethics Committee (IRB/IEC) approval/favorable opinion before initiation of the study.

All potential serious breaches must be reported to Bristol-Myers Squibb (BMS) immediately. A serious breach is a breach of the conditions and principles of GCP in connection with the study or the protocol, which is likely to affect, to a significant degree, the safety or physical or mental integrity of the subjects of the study or the scientific value of the study.

Study personnel involved in conducting this study will be qualified by education, training, and experience to perform their respective tasks. This study will not use the services of study personnel where sanctions have been invoked or where there has been scientific misconduct or fraud (eg, loss of medical licensure; debarment).

3.2 Institutional Review Board/Independent Ethics Committee

Before study initiation, the investigator must have written and dated approval/favorable opinion from the IRB/IEC for the protocol, consent form, subject recruitment materials/process (eg, advertisements), and any other written information to be provided to subjects. The investigator should also provide the IRB/IEC with a copy of the Investigator Brochure or product labeling, information to be provided to subjects, and any updates. The investigator should provide the IRB/IEC with reports, updates, and other information (eg, expedited safety reports, amendments, and administrative letters) according to regulatory requirements or institution procedures.

3.3 Informed Consent

Investigators must ensure that subjects (or, in those situations where consent cannot be given by subjects, the legally acceptable representative) are clearly and fully informed about the purpose, potential risks, and other critical issues regarding clinical studies in which they volunteer to participate. Freely given written informed consent must be obtained from every subject (or, in those situations where consent cannot be given by subjects, the legally acceptable representative) before clinical study participation, including informed consent for any screening procedures conducted to establish subject eligibility for the study.

Investigators must:

- 1) Provide a copy of the consent form and written information about the study in the language in which the subject is most proficient prior to clinical study participation. The language must be non-technical and easily understood.
- 2) Allow time necessary for subject or subject's legally acceptable representative to inquire about the details of the study.
- 3) Obtain an informed consent signed and personally dated by the subject or the subject's legally acceptable representative and by the person who conducted the informed consent discussion.
- 4) Obtain the IRB/IEC's written approval/favorable opinion of the written informed consent form and any other information to be provided to the subjects, prior to the beginning of the study, and after any revisions are completed for new information.
- 5) If informed consent is initially given by a subject's legally acceptable representative or legal guardian, and the subject subsequently becomes capable of making and

communicating their informed consent during the study, then consent must additionally be obtained from the subject.

- 6) Revise the informed consent whenever important new information becomes available that is relevant to the subject's consent. The investigator, or a person designated by the investigator, should fully inform the subject or the subject's legally acceptable representative or legal guardian, of all pertinent aspects of the study and of any new information relevant to the subject's willingness to continue participation in the study. This communication should be documented.

The consent form must also include a statement that BMS and regulatory authorities have direct access to subject records.

The rights, safety, and well-being of the study subjects are the most important considerations and should prevail over interests of science and society.

4 INVESTIGATIONAL PLAN

4.1 Study Design and Duration

Subjects:

40 obese subjects with impaired glucose tolerance (IGT) or prediabetes, (fasting plasma glucose between 100-125 mg/dl, or 2 hour post 75 gram OGTT plasma glucose between 140-199 mg/dl, or HbA1c 5.7-6.4%) who are free of other major organ system disease will be studied. Subjects will range in age from 30 to 70 years and in body mass index from 30-35 kg/m². Subjects who have previously received or are taking metformin, DPP-IV inhibitors, exenatide, liraglutide, or a thiazolidinedione for treatment of IGT will be excluded. Patients on statins and other lipid lowering therapy will be included provided they are on a stable dose of lipid lowering therapy for at least 3 months prior to enrollment. The dose of the lipid lowering therapy will not be changed for the entire duration of the study. The fasting plasma glucose must be ≤ 125 mg/dl, 2 hour post 75 gram OGTT plasma glucose must be less

than 200 mg/dl, and HbA1C must be < 6.5% to be included in the study. Subjects with clinically significant cardiac, hepatic, or renal disease will not be studied. Subjects will be recruited from the Endocrine/Diabetes/Obesity Clinic at the Baylor Clinic. All subjects will be recruited by direct contact from [name] or one of the co-investigators.

Study Design: All subjects will participate in an initial screening visit (medical history and physical exam, urinalysis, EKG, CBC, liver function tests (LFTs), serum creatinine, lipid profile, HbA1c; and a fasting and 2 hour plasma glucose (during a 75 gram OGTT). During the 2 hour OGTT (75 grams), glucose, insulin, c-peptide, and FFA determinations will be made at baseline (fasting) and every 15-30 minutes and insulin sensitivity will be calculated by the Matsuda Index. In addition, plasma triglycerides will be measured at baseline and at 120 minutes during the OGTT.

Following determination of eligibility, 40 IGT or prediabetes subjects will be randomized (double blind) to participate in one of the following two treatment arms (i) saxagliptin 5 mg daily PO for 26 weeks or (ii) Placebo PO daily for 26 weeks (control arm). Two weeks prior to randomization, subjects will meet with a dietitian and will be instructed to consume a weight-maintaining diet containing 50% carbohydrate, 30% fat, and 20% protein. During the week prior to start of the study all subjects will receive: (i) baseline measurements of FPG, plasma adiponectin (HMW and total adiponectin), CRP, IL-1, IL6, TNF-alpha, MMP-9, ICAM, VCAM, Fibroblast Growth Factor 21 (FGF21), fasting

plasma lipids, postprandial plasma triglyceride level (at 2 hours following a mixed meal), and HbA1c; (ii) monocyte isolation from peripheral (venous) whole blood and quantification of monocyte TLR2, TLR4, SOCS-3, MYD88, NFkappaB (P65) and Ikb-alpha, and Ikb-beta protein as well as expression levels of CD36, MCP-1, MMP-9, VCAM1, ICAM1 and JNK. We will also measure of plasma lipopolysaccharide (LPS) and LPS- binding protein (LPS-BP) concentrations. Plasma samples used for LPS determination will be stored in LPS-free glass tubes to prevent loss of endotoxin to plastic tube walls. All materials for the assay will be rendered LPS-free; and (iii) liver and myocardial fat content with magnetic resonance (MR) spectroscopy and determination of left ventricular systolic and diastolic function by MR imaging as detailed below.

During the entire 6 month treatment period, subjects will return to the Clinical Research Center every 4 weeks at 0800 h following an overnight fast for measurement of FPG, body weight, and blood pressure. A urine pregnancy test will also be performed at each visit. On each visit, dietary adherence will be reinforced by the dietician. Fasting plasma lipids and postprandial triglyceride levels, HbA1c, and LFTs will be measured at 3 months and at the end of the 6 month study period. At the end of the treatment period of six months all subjects will also undergo a repeat 75 gram OGTT (for measurements of baseline FPG, and plasma glucose, FFA, c-peptide and insulin during OGTT as well as 2 hour plasma triglyceride measurements as described previously), plasma adiponectin,

CRP, IL-1, IL6, TNF-alpha, MMP-9, ICAM, VCAM, Fibroblast Growth Factor 21 (FGF21), FFA, insulin, LPS and LPS-BP. Liver and Myocardial fat and LV function as well as monocyte studies for inflammatory pathways as detailed previously will be repeated after 26 weeks of therapy.

Measurement of Liver Fat Content (MR Spectroscopy)

Localized ¹H nuclear magnetic resonance spectra of the liver will be obtained on a 3.0 Tesla magnetic resonance imaging scanner (Department of Radiology, St Lukes Episcopal Hospital and Texas Heart Institute, Houston) using a standard body coil in transmitter and receiver mode. An initial T1-weighted spin-echo anatomical magnetic resonance scan for liver MRS localization will be performed with the following parameters: repetition time/echo time = 130 msec/15 msec; 160 degrees; slice thickness = 7 mm; field of view = 44 cm x 45 cm; number of excitations = 1; and an image matrix = 100 x 256. The slice with the largest gross dimensions of the liver will be chosen for the MRS study. MRS for water and fat quantification will be accomplished by using a point resolved spectroscopy sequence as described previously (3). The imaging parameters for point resolved spectroscopy sequence are as follows: repetition time/echo time = 1500 msec/54 msec; 90 degree; number of averages = 2; and data points = 512. A 3 cm x 3 cm x 3 cm volume (voxel) will be selected in the left, right anterior, and right posterior hepatic lobes for scanning to provide a more generalized distribution of fat within the liver. During the measurements, the

subject will be supine within the bore of the magnet. The total scan time is approximately 60 min. During the MRS examinations, identical areas of the liver are scanned in the pre- and post-treatment MRS studies of the same subject by the use of anatomical landmarks visualizing images.

After line broadening, phase and baseline correction, the peak area of the water at 4.77 ppm, and fat resonance (Sf) at 1.4 ppm will be measured. Quantification of the fat content will be done by comparing the area of the Sf with that of the unsuppressed water. Spectroscopic data will be processed using the operating system software. Hepatic fat percentage will be calculated by dividing $(100 \times \text{Sf})$ by the sum of Sf and peak area of the water. This technique is highly reproducible, with a coefficient of variation less than 2% when the same subjects were studied on eight separate days.

Measurement of Cardiac Myocardial Triglyceride Content with Dual Gating

The MR studies will be performed on a commercial MR scanner (3.0 tesla) equipped with 1H MR Spectroscopic capabilities. The participating subjects will undergo MR scanning in the morning after fasting overnight. A 5-10 ml size voxel will be carefully positioned over the interventricular septum based on the four-chamber and the short-axis images acquired at end-systole. Based on a high-temporal resolution cine image acquired previously, the MR spectroscopy will be timed to occur during systole, and MR spectra will be acquired using the following acquisition parameters: sequence type: Point resolved

spectroscopy sequence (PRESS); TE: 25 ms; TR > 3000 msec; 1024 acquisition points acquired using 1 kHz spectral bandwidth, and 128 NSA. The long TR ensures a more complete recovery of the myocardial triglyceride signals. The cardiac MR spectroscopy sequence is both cardiac gated (vectorcardiography (VCG) gating), as well as respiratory gated to combat the adverse effects of both cardiac pulsation as well as bulk motion of the heart caused by respiratory motion. Gating (respiratory and cardiac gating) improves the reproducibility of cardiac MR spectra. During the MRI/MRS, we will also measure LV systolic and diastolic function.

MRI Measurement of Left Ventricular Function

Systolic LV Function: A series of scout images of the thoracic cavity along multiple axes will be obtained. Following these scout scans, a series of cardiac cine Steady State Free Precession (SSFP) images will be obtained along the conventional two-chamber and four-chamber orientations with the following acquisition parameters: TR/TE/flip: 3-3.2 ms/1.5-1.6 ms/; slice thickness: 8 mm; temporal resolution: 40-50 ms; acquired in-plane spatial resolution: 2 x 2 mm; breath-hold duration: 6-8 heart-beats per slice. Based on these two long-axis orientation slices, a series of contiguous short-axis slices were acquired to cover from the left-ventricular apex to the base at 8 mm intervals in a series of breath-holds. The endocardial contours will be manually traced by an experienced observer at end-diastole and end-systole to delineate the LV volume in diastole (EDV) and systole (ESV). From the knowledge of EDV, and

ESV, LV ejection fraction (LVEF) will be calculated as the normalized difference between EDV and ESV, or $(EDV-ESV)/EDV$.

Diastolic LV function: MRI flow measurements: Diastolic LV function will be obtained by measuring the blood-flow across the mitral-valve using a cardiac-gated phase-contrast MR sequence. A 5 mm slice oriented orthogonal to the mitral valve plane (positioned with the help of the four-chamber and the left-ventricular outflow tract (LVOT) views) will be acquired with the following parameters: TR/TE: 4.6 ms/15 ms; flip angle; in-plane acquired voxel size: 1.6 x 1.8 mm; reconstructed voxel size: 1.2 x 1.2 mm; velocity encoding value (Venc value): 100-125 cm/s; number of acquisitions: 2. The acquisition will be retrospectively cardiac gated to ensure that the entire diastolic period is captured.

MRI flow analysis: The flow data will be analyzed using a commercial post-processing workstation. The characteristic diastolic flow data will be quantified by calculating the peak filling rates during the early filling phase (E), and the active filling phase (A).

High temporal resolution cine MR imaging:

Using a combination of a state-of-the-art RF hardware (32 channel RF system), and fast imaging techniques (Sensitivity Encoding or SENSE), a high temporal resolution cine MR images (~ 6 ms/cardiac phase) of the LV will be acquired in a series of breath-holds. A total of three short-axis slices will be acquired with a temporal resolution of 5-6.5 ms using the following acquisition parameters: TR/TE/flip: 2.7-3.1 ms/1.5-1.6 ms; acquired voxel size: 2.5 x 2.5 x 8 mm; reconstructed voxel size: 1.76 x

1.76 x 8 mm; half-scan factor: 0.625; number of phase encoding steps acquired per heart-beat (turbo-field echo factor): 2; acquired temporal resolution: 5.5 – 6.2 ms/cardiac phase; SENSE factor: 3; total scan time: 18-20 hb/slice. From the high-temporal resolution cine images, the LV cavity will be segmented using a segmentation algorithm. Metrics quantifying diastolic function such as IVRT will be calculated using custom-built software. A series of blood-pressure measurements will be obtained throughout imaging at 5 minute intervals.

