6.4.2 Secondary Efficacy Assessments

The secondary efficacy objective is to determine whether treatment with saxagliptin compared with placebo will result in an improvement in left ventricular systolic and diastolic function and a reduction in monocyte inflammation in patients with IGT.

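### The transmitral phase-contrast slice in section 4.1 is placed orthogonal to the mitral valve plane, so it cannot give the through-plane E and A filling rates named as its output; the printed TR/TE also needs checking

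*Combined protocol and SAP*

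**What the plan says.** Section 6.4.2 makes "improvement in left ventricular systolic and diastolic function" a secondary efficacy objective, and section 8.3 repeats it as part of the secondary endpoint. Section 4.1, under the heading on MRI flow measurements, obtains diastolic function by "measuring the blood-flow across the mitral-valve using a cardiac-gated phase-contrast MR sequence". The acquisition is described as "A 5 mm slice oriented orthogonal to the mitral valve plane", positioned from the four-chamber and LVOT views. The settings include "TR/TE: 4.6 ms/15 ms" and "velocity encoding value (Venc value): 100-125 cm/s; number of acquisitions: 2". No direction of velocity encoding is given. The flow analysis then consists of "calculating the peak filling rates during the early filling phase (E), and the active filling phase (A").

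Section 4.1 also describes a separate high-temporal-resolution cine, for which "Metrics quantifying diastolic function such as IVRT will be calculated using custom-built software". Table 1 in section 6.1 schedules the MRI studies at Visit 3 (week -1) and Visit 11 (week 26). For liver spectroscopy, section 4.1 requires the same regions to be scanned before and after treatment, using anatomical landmarks. It has no matching rule for the flow slice.

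**The concern.** The prescribed slice and the quantity to be derived from it do not fit together. A filling rate is a volume per unit time through the valve orifice. Phase-contrast MR obtains it by encoding velocity perpendicular to a slice that cuts across the whole stream. A slice orthogonal to the valve plane runs along the stream instead. Separately, the printed echo time exceeds the repetition time, which a conventional phase-contrast gradient-echo scan cannot run.

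E and A are two of the diastolic measures that the protocol names. LV function also enters the planned correlations with fat content in section 8.4.2. Staff who cannot follow the text as written must choose a plane and timing themselves, and nothing written requires the same choice at both visits, 26 - (-1) = 27 weeks apart. The analysis looks at change over time with 32 completers planned (section 8.1), so avoidable measurement variation matters.

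**Working it through.** The plan gives no figure of its own on this point, so there is none to reproduce. Two checks apply. The first uses general imaging geometry, not a number from the documents.

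**1. Slice orientation**

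- Inputs from section 4.1: slice orthogonal to the valve plane, 5 mm thick; output E and A peak filling rates; encoding direction unstated.
- Assumption: inflow is roughly perpendicular to the valve plane.
- Filling rate = sum over the orifice of (velocity component along the slice normal × area). With θ the angle between slice normal and inflow, the recorded share of the velocity is cos θ.
- Slice parallel to the valve plane: θ = 0°, share 1.00. With 10°, 20° or 30° of tilt it is 0.985, 0.940 or 0.866.
- Slice as written: θ = 90°, share cos 90° = 0.
- Range for the assumption: if the inflow leans δ away from the perpendicular, the written slice records at most cos(90° - δ). That is 0.17 at δ = 10°, 0.34 at 20° and 0.50 at 30°. Even then the slice meets the orifice only along a 5 mm strip and does not span it.
- Alternative reading: with velocity encoded in-plane along the inflow, the written slice could record E and A velocities. It still would not give flow through the whole orifice.

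**2. TE against TR for every MR sequence in section 4.1**

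| Sequence | TR (ms) | TE (ms) | TE/TR |
|---|---|---|---|
| Liver localiser | 130 | 15 | 0.115 |
| Liver spectroscopy | 1500 | 54 | 0.036 |
| Cardiac spectroscopy | >3000 | 25 | <0.009 |
| SSFP cine | 3-3.2 | 1.5-1.6 | 0.469 to 0.533 |
| High-temporal-resolution cine | 2.7-3.1 | 1.5-1.6 | 0.484 to 0.593 |
| Flow scan as printed | 4.6 | 15 | 3.261 |

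Only the flow scan has TE above TR. If the two values were exchanged, the ratio would be 4.6/15 = 0.307. If a decimal point were lost from TE, it would be 1.5/4.6 = 0.326. Either would be in line with the other sequences, and the documents do not say which applies.

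**The case against.** The case on the other side has real force.

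- **Intent.** The text says the aim is flow across the valve and plans the slice from two long-axis views, which is how one would set a slice across the inflow. The wording may be a slip for orthogonal to the inflow, and experienced staff may already acquire the right plane. This is plausible, but no other section says so, and the sentence as written gives the wrong plane for the stated output.
- **Encoding direction.** A reader might infer that the scan cannot measure mitral inflow at all. The documents do not support that: the encoding direction is open, and in-plane encoding could give E and A velocities. The point stands only against the filling rates that the protocol names. If the sponsor means peak velocities, the text must say so.
- **TR/TE.** A reader might take TE above TR as evidence that E and A would be invalid in both arms. It is not. A pair that cannot be run produces no data, so workable values would have to be set at the scanner. The flip angle in the same parameter list has no value, which suggests loss in reading the PDF, and the TE figure could have the same cause. This item is a documentation matter to verify.
- **Drift between visits.** Nothing shows that settings would differ between Visits 3 and 11. In a single-centre, randomised, double-blind trial, such variation would mainly add noise to both arms and not bias the comparison. What remains is that no written rule prevents it.

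**Conclusion.** The point holds in limited form, at moderate severity. As written, the slice cannot yield a through-plane filling rate: the recorded share of the inflow velocity is 0 under the perpendicular-inflow assumption, against at least 0.866 for a parallel slice within 30° of tilt. With in-plane encoding it could give at most E and A velocities. The printed TR/TE is inconsistent with the five other sequences and is probably a transcription error or PDF loss.

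A reader might also infer that the diastolic endpoint is lost, or that a fixed fraction of its measures is. Neither follows. IVRT comes from the separate cine, and the protocol names it only as an example, so the list of diastolic measures is open and no denominator can be set. LVEF comes from the SSFP cine volumes. The primary fat endpoints come from spectroscopy, and the sample size in section 8.1 rests on those alone. What is affected is one component of a secondary endpoint.

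**What to change.** In section 4.1, under MRI flow measurements:

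1. Place the slice parallel to the mitral valve plane, perpendicular to the inflow as seen on the four-chamber and LVOT views.
2. State that velocity is encoded through-plane.
3. Check TR/TE against the source document and the scanner protocol, and correct it so that TE is below TR.
4. Require the same plane and settings at Visits 3 and 11 for each patient, as the protocol already does for the liver regions.

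The cost is a few lines of text and one check of the scanner protocol. No extra scan time, staff or patients are needed.

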4.2 Study Population

For entry into the study, the following criteria MUST be met.

